9.2 SAMPLE SIZE DETERMINATION

Statistical power to identify effects of the nudges was examined using recent past data from the participating hospitals. We estimated design parameters required by the PowerUpR package in R software,⁴⁸ which provides the capability to estimate statistical power for randomized block clustered designs. Examining medication dose, input parameters for the calculation included unconditional intracluster correlations (ICC) for the hospital (ICC=0.005), service line (ICC=0.039), and provider (ICC=0.337) levels; the number of service line groups (up to three per hospital); the number of providers by service line expected to participate in the study; and number of patients per service line. The ICCs were empirically determined from our preliminary data. We assumed that covariates informative of the dosage would explain between 25 percent and 50 percent of the dosage variation at each of the patient, provider, and service line levels (i.e., R^2 between 0.25 and 0.50). We derived statistical power, assuming one third of the service line groups within hospital will be randomly assigned to each study arm (two treatment and one control). We computed power for pairwise comparison of each of the two nudge arms versus the no nudge arm and adjusted our alpha level to account for multiple comparisons (alpha=0.05/2). We will have 80% power to detect significant differences between the intervention conditions of at least a minimum detectable effect size (MDES) = 0.347 standard deviations (SDs) when $R^2=0.25$, while $R^2=0.5$ would yield a MDES of 0.305.

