4.3 JUSTIFICATION FOR DOSE

Using prescribing data from recent years at Sutter Health, we simulated how many surgeons would receive nudges and how many nudges they would receive under different study design parameters. From this we determined that delivering the nudges monthly achieved a balance between exposing them to the intervention and burdening them with emails. We chose to deliver the nudges by email because this method presents a low burden to surgeons, has been successful in a similar study conducted at Sutter Health,⁴⁵ and would be easily scalable beyond Sutter Health if our nudges prove effective.

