6 STUDY INTERVENTION

6.1 STUDY INTERVENTION(S) ADMINISTRATION

6.1.1 STUDY INTERVENTION DESCRIPTION

Surgeons randomized to our study intervention will receive one of two types of behavioral nudges delivered as monthly emails. The two nudges will be active for twelve months (October 2021–October 2022).

To ensure that the nudges target only *inappropriate* opioid prescribing, surgeons will receive nudges only when they write opioid prescriptions that exceed post-operative opioid prescribing guidelines developed by multidisciplinary teams at the Mayo Clinic.^{32, 46, 47} (and personal communication with [name], Ph.D., MPH, on opioid prescribing guidelines for caesarean section, March 12, 2021; unreferenced) These guidelines recommend ranges of 5mg oxycodone tablet quantities specific to the procedure performed and are partly based on patient surveys of actual post-operative opioid use.

In both nudge conditions, eligibility for receiving a monthly nudge is contingent upon at least two of the surgeon's patients being discharged with a post-operative opioid prescription exceeding the quantities specified by the Mayo Clinic guidelines. Though it may seem counterintuitive for the descriptive norm nudge to be based implicitly on prescribing guidelines, this choice ensures patient safety and avoids confounding the content of the nudge with the threshold for receiving a nudge.

Intervention arm 1: nudge based on descriptive norms

Surgeons randomized to this condition will receive an email with the following content at the end of each month in which at least two of their patients are discharged with a post-operative opioid prescription that exceeds the prescribing guideline for the procedure performed.

[Subject line: Your peers vs. your opioid prescribing safety record]

Dear Dr. [Name],

In an effort to reduce opioid use among our surgical patients, Sutter Health is reviewing opioid prescriptions and prescribing patterns for surgeons and will be communicating the findings.

In [month], at least **XX** of your patients were discharged with opioid prescriptions **exceeding** the amount prescribed by **YY%** of your peers for these procedures.

YY% of [specialty] surgeons at Sutter Health prescribe within the ranges below.

We will continue to send you opioid prescribing safety reports.

Sincerely,

[Signature(s) of chief medical executive, chief of staff, and/or surgical department chair at the surgeon's hospital]

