9 STATISTICAL CONSIDERATIONS

9.1 STATISTICAL HYPOTHESES

The null hypotheses are that (1) $\beta_1 = 0$, (2) $\beta_2 = 0$, and (3) $\beta_1 = \beta_2$ in the hierarchical linear model

$$Y_{ipsh} = \beta_0 + \beta_1 ARM1_{sh} + \beta_2 ARM2_{sh} + \gamma_{1h} ARM1_{sh} + \gamma_{2h} ARM2_{sh} + \omega_1 X_{ipsh} + \omega_2 Z_{psh} + \omega_3 U_{sh} + \omega_4 W_h + \gamma_h + \eta_{sh} + \varphi_{psh} + \varepsilon_{ipsh}, \quad (1)$$

where i is the patient treated by surgeon p in specialty s at hospital h , $ARM1_{sh}$ and $ARM2_{sh}$ are indicator variables for whether specialty s at hospital h were assigned to intervention arm one or two respectively, X is a set of patient covariates, Z is a set of surgeon covariates, U is a set of specialty covariates, and W is a set of hospital covariates.

The alternative hypotheses are that (1) $\beta_1 \neq 0$, (2) $\beta_2 \neq 0$, and (3) $\beta_1 \neq \beta_2$.

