9.3 POPULATIONS FOR ANALYSES

Our main analyses will be conducted on an intention-to-treat dataset including all randomized surgeons. Sensitivity analyses may be conducted on a dataset excluding surgeons who received no nudges.

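### Section 9.2 gives an arm-average detectable effect without the share of discharges exposed to an email, and the only exposure-based analysis (9.3) has no valid control group

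*Combined protocol and SAP*

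**What the plan says.** Section 9.2 begins: "Statistical power to identify effects of the nudges was examined using recent past data from the participating hospitals". It then reports: "We will have 80% power to detect significant differences between the intervention conditions of at least a minimum detectable effect size (MDES) = 0.347" SD at R² = 0.25, and says that R² = 0.5 "would yield a MDES of 0.305". The outcome used is medication dose. The listed inputs are intracluster correlations, R², and numbers of service lines, providers and patients. No exposure share is among them.

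Section 6.1.1 makes the email conditional: "eligibility for receiving a monthly nudge is contingent upon at least two" of the surgeon's patients going home with a prescription above guideline. Section 7.2 also lets surgeons unsubscribe.

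Section 9.3 bases the main analyses on an "intention-to-treat dataset including all randomized surgeons", and section 9.4.2 tests each arm's coefficient against control. Section 9.3 also allows, without committing to it, a sensitivity analysis that leaves out surgeons who were never nudged.

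The sponsor evidently expects some surgeons in the nudge arms to receive nothing. Section 4.3 says "we simulated how many surgeons would receive nudges and how many nudges they would receive under different study design parameters", and section 8.2 sets up separate safety reports for surgeons who were ever emailed. Section 9.4.6 plans an interaction with the surgeon's baseline above-guideline share and predicts a larger effect where that share is higher.

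**The concern.** Power is introduced as power for effects of the nudges, but the figure is an average over everyone in the arm. That average includes surgeons who never reach the two-discharge trigger and discharges that precede a surgeon's first email. If those contribute no effect, the effect on emailed surgeons must exceed 0.347 SD for the arm average to reach it. Without the exposed share, a reader cannot judge whether an arm average of 0.305 to 0.347 SD is attainable. Nor can a reader of a null result tell ineffective emails from infrequent ones.

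Section 4.2 says that the trial is meant to support a recommendation on investing in such nudges, so that distinction will be wanted. The plan's one analysis aimed at it, in 9.3, is not a randomised comparison.

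**Working it through.** **Inputs.** From 9.2: MDES 0.347 SD (R² = 0.25) and 0.305 SD (R² = 0.50); 80% power; alpha 0.05/2 = 0.025 per comparison; ICCs 0.005 (hospital), 0.039 (service line) and 0.337 (provider). From 9.1: two-sided alternatives. From 4.1: 19 hospitals. Assumed, because the documents give no value: f, the share of a nudge arm's analysed discharges that follow the surgeon's first email.

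**1. The plan's own figure.** For a blocked cluster design,

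MDES = M × √[ρ₄ω/L + {ρ₃(1−R²)/K + ρ₂(1−R²)/(JK) + ρ₁(1−R²)/(JKn)} / (P(1−P)L)],

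with L = 19 hospitals, K service lines per hospital, J surgeons per line, n patients per surgeon, P the proportion treated, ω the effect-heterogeneity ratio, M the sum of the two t quantiles, and ρ₁ = 1 − 0.005 − 0.039 − 0.337 = 0.619. J, n and ω have no stated values, so the figure cannot be reproduced.

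- Guessing K = 2, P = 1/2, J = 4, n = 10, ω = 0.5 and 18 df gives 0.348 at R² = 0.25, but 0.285 rather than 0.305 at R² = 0.50.
- The stated ratio is 0.305/0.347 = 0.879, against √(0.50/0.75) = 0.816 if every term scales with 1−R².
- Applying R² only at patient and provider level (J = 3.5, n = 100, ω = 0, 36 df) gives 0.347 and 0.307.

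These inputs are guesses, so they neither confirm nor contradict the stated figures. The next steps take 0.347 and 0.305 as given.

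**2. Implied standard error.** z(0.9875) + z(0.80) = 2.241 + 0.842 = 3.083, so SE = 0.347/3.083 = 0.113 SD (0.305/3.083 = 0.099 SD).

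**3. Dilution.** If the effect equals the MDES on a share f of discharges and zero on the rest, the arm contrast is f × MDES. Then power = Φ(3.083f − 2.241), which is the same for 0.347 and 0.305. The effect on exposed discharges that restores 80% power is MDES/f.

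| f | Power | MDES/f, R² = 0.25 | MDES/f, R² = 0.50 |
|---|---|---|---|
| 1.00 | 80% | 0.347 | 0.305 |
| 0.95 | 75% | 0.365 | 0.321 |
| 0.90 | 70% | 0.386 | 0.339 |
| 0.75 | 53% | 0.463 | 0.407 |
| 0.50 | 24% | 0.694 | 0.610 |

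Power is exactly 50% at f = 2.241/3.083 = 0.727. Noncentral t calculations with 18 or 36 df agree within 0.3 points.

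**4. The 9.3 sensitivity set.** Controls receive no nudges by design. Read literally, the exclusion removes every control surgeon. Applied to the nudge arms alone, it keeps surgeons who had at least two above-guideline discharges in some month after randomisation. That selects on the behaviour the primary endpoint measures, leaves heavier prescribers in the nudge arms, and compares them with unselected controls.

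**5. A baseline-defined set.** Choosing surgeons in all three arms by whether they met the trigger before the intervention keeps the randomised comparison. To see the direction of any gain, use the formula in step 1 with J = 4, n = 30, K = 2, P = 1/2, ω = 0.5, R² = 0.25 and 18 df. Assume a true effect of 0.347 SD in triggered surgeons, equal volumes, and baseline status that identifies later recipients perfectly. Here f is a share of surgeons, and the restricted set has fJ surgeons per line.

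| f | SE, all | Power, all | SE, restricted | Power, restricted |
|---|---|---|---|---|
| 0.7 | 0.101 | 50% | 0.115 | 71% |
| 0.5 | 0.101 | 26% | 0.132 | 58% |

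The smaller set costs precision but loses less than dilution does. J, n and perfect identification are assumed, so only the direction should be relied on.

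**The case against.** The strongest reply is that 9.2 is right on its own terms. A reader might infer that the calculation gives every randomised surgeon the full nudge effect. The text does not say so: it claims power for differences between conditions, which matches the arm coefficients in 9.4.2 and the intention-to-treat population in 9.3. That stands.

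A reader might also infer that real power is far below 80%, or that a worthwhile effect on emailed surgeons would usually be missed. The documents do not support this either. Power below 50% needs f below about 0.73, and no section gives f. Surgeons who reach the trigger may carry more of the discharges, which raises f, while discharges before a first email lower it. Because a whole specialty at a hospital shares an arm, spillover to colleagues who were not emailed could reduce dilution further.

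It is also fair to say that the trigger is part of the intervention, so the arm average is the right quantity for the investment question in 4.2. That supports keeping intention-to-treat as primary. It does not explain what a null result would mean.

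Finally, 9.4.6 already plans an interaction with baseline prescribing. It is sound and uses pre-intervention data, but it works on the share above guideline rather than a count of two in a month. A low-volume surgeon with a high share may never trigger, and a high-volume surgeon with a modest share may. It therefore does not isolate the surgeons likely to be emailed.

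**Conclusion.** The point holds as a gap in interpretation and in the supporting analysis, not as an error in the power calculation. The 0.347 and 0.305 SD figures are legitimate arm-average effects for dose. They are not translated into an effect on exposed discharges, although the sponsor has simulated exposure.

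If the effect is confined to exposed discharges, power for the stated MDES among them is below 80% for any f under 1. The loss is about 5 points at f = 0.95 and 10 at 0.90, but 27 at 0.75 and 56 at 0.50. This rests on f, which is assumed, on zero effect elsewhere, and on the stated MDES, power and alpha. The percentages apply to dose and do not carry over as numbers to the binary primary endpoint.

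The flaw in the 9.3 sensitivity set does not depend on f.

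**What to change.** 1. Keep the intention-to-treat analysis as primary.
2. In 9.3, replace the optional exclusion of never-nudged surgeons with one pre-specified supporting analysis: surgeons in all three arms who met the two-discharge trigger in at least one month of the baseline period (before 19 October 2021; 9.4.4 ends baseline on 18 October). Section 5.5 enrols surgeons already present in the record from June 2020 to May 2021, so baseline data should exist for all of them. Report the result alongside the 9.4.6 baseline-prescribing interaction.
3. In 9.2, label 0.347 and 0.305 SD as arm-average effects on dose. Take f from the 4.3 simulation, run under the current trigger, and report MDES/f.

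The cost is a few sentences, reuse of an existing simulation and one extra model on data already collected; sample size and primary analysis are unchanged. The downsides are that the supporting result applies only to surgeons likely to be emailed, and that some dilution remains from discharges before a surgeon's first email.

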9.3 POPULATIONS FOR ANALYSES

Our main analyses will be conducted on an intention-to-treat dataset including all randomized surgeons. Sensitivity analyses may be conducted on a dataset excluding surgeons who received no nudges.

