1.2 SCHEMA

1.3 SCHEDULE OF ACTIVITIES (SOA)

Nudges will be delivered on the third Tuesday of each month for 12 months, October 2021 through September 2022. Data will be collected continuously, with data from the first through last day of the previous calendar month informing whether a nudge is triggered and, if so, the content of the nudge.

After 12 months, the nudges will stop, but data will be collected continuously for another 12 months to assess the persistence of any effects of the nudges.

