[Table including each procedure type performed by this surgeon in the reference month and the corresponding "Amount prescribed by your peers (5mg oxycodone tablets)", with a footnote stating the conversion factors for hydrocodone and tramadol]

The ranges of 5mg oxycodone tablets displayed in the email will be the same as the ranges stipulated by the prescribing guidelines, but this nudge will not include any language about guidelines.

Intervention arm 2: nudge based on injunctive norms

This condition will be identical to the first condition, except the content of the monthly emails will refer to safety guidelines rather than the surgeon's peers.

[Subject line: Best practice guidelines vs. your opioid prescribing safety record]

Dear Dr. [Name],

In an effort to reduce opioid use among our surgical patients, Sutter Health is reviewing opioid prescriptions and prescribing patterns for surgeons and will be communicating the findings.

In [month], at least **XX** of your patients were discharged with opioid prescriptions **exceeding** the amounts recommended by safety guidelines for these procedures.

For patient safety, Sutter Health recommends prescribing within the ranges below for these procedures. Doing so will also meet best practice safety guidelines for post-operative opioid prescribing.

We will continue to send you opioid prescribing safety reports.

Sincerely,

[Signature(s) of chief medical executive, chief of staff, and/or surgical department chair at the surgeon's hospital]

[Table including each procedure type performed by this surgeon in the reference month and the corresponding "Amount recommended by Sutter Health (5mg oxycodone tablets)", with a footnote stating the conversion factors for hydrocodone and tramadol]

Control arm

Surgeons randomized to the control arm will not receive any nudges and will not be informed of the study. By not informing them of the study, we will prevent a Hawthorne effect and obtain an accurate representation of status quo prescribing behavior against which to test the effects of the nudges.

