9.4.2 ANALYSIS OF THE PRIMARY AND SECONDARY EFFICACY ENDPOINTS

Our primary outcome is the share of discharge prescriptions that were above the guideline for the respective procedure (see above for how guidelines were identified). Prescribing above guidelines is the outcome to which both nudges are linked (even though the descriptive norm nudge does not explicitly refer to guidelines) and thus a key measure of whether clinician behavior responds to the nudges. We define a prescription as being above guidelines if the morphine milligram equivalent (MME) quantity of opioids prescribed is above the ceiling for the procedure-specific guideline (guidelines range from zero to a ceiling). If no opioid is prescribed at discharge, we will code this as within guideline.

We will also analyze the following secondary outcomes to further understand the effects of the intervention.

- MMEs prescribed at discharge
- Days' supply of opioids prescribed at discharge
- Share of discharges where any opioid was prescribed
- Share of patients on opioids for greater than three months post-discharge
- Number of 30-day all-cause emergency department visits
- Number of 30-day all-cause hospitalizations
- Share of discharge opioid prescriptions above prescribing guidelines in the 12 months after the nudges end

Primary analysis

We will analyze outcomes at the level of the discharge using a four-level hierarchical linear model (HLM),[42] thus capturing the clustering inherent in the study design and data generating process. We will analyze outcomes at the patient level, and patients are nested within surgeons, who are nested within specialties, which are nested within hospitals. Both primary and secondary outcomes will follow this modeling structure. To improve the precision of our estimates, we will also include a set of observable patient covariates (X), surgeon covariates (Z), specialty covariates (U), and hospital covariates (W). For patient i , treated by surgeon p , in specialty s , at hospital h , we consider the following HLM formulation for continuous outcomes Y_{ipsh} :

$$Y_{ipsh} = \beta_0 + \beta_1 ARM1_{sh} + \beta_2 ARM2_{sh} + \gamma_{1h} ARM1_{sh} + \gamma_{2h} ARM2_{sh} + \omega_1 X_{ipsh} + \omega_2 Z_{psh} + \omega_3 U_{sh} + \omega_4 W_h + \gamma_h + \eta_{sh} + \varphi_{psh} + \varepsilon_{ipsh} \quad (1)$$

$ARM1_{sh}$ and $ARM2_{sh}$ are indicator variables for whether specialty s , at hospital h were assigned to intervention arm one or two respectively.

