The key terms in the equation are β_1 and β_2 , the covariate-adjusted treatment effects of arms 1 and 2 relative to the control arm; β_1 answers research question 1 and β_2 answers research question 2. We will use an F-test to compare coefficients β_1 and β_2 to answer research question 3. Thus, the effect of each nudge is estimated relative to receiving no nudges and to the other nudge.

The model allows for the possibility that the treatment effect varies across hospitals, as captured by the random effects (γ_{1h}, γ_{2h}). Unexplained variation in each of the levels is captured by the random effects $\varepsilon_{ipsh}, \varphi_{psh}, \eta_{sh}$, and γ_h . We will initially model these six random effects as independent but will also investigate whether including a covariance structure across these components is appropriate. The coefficients ω_1, ω_2 , and ω_3 , capture the influence of the covariates at the patient, surgeon, and specialty respectively, and covariates will be mean centered as appropriate to aid in model

interpretation. Covariates may include but are not limited to the following: Level 1: patient age, patient sex, patient comorbidities, procedure type, length of operating time; Level 2: surgeon sex, year of surgeon's medical degree; Level 3: total volume of procedures within the specialty; Level 4: number of beds, urbanicity, proportion of patients on Medicaid. Given that the covariates will not change the estimate of the treatment effect (in expectation), only reduce unexplained variance, we will choose a final pool of covariates that we find to be predictive the primary outcome. Model estimates of the treatment effects will adjust standard errors for clustering due to the due to clustered assignment of the interventions.

For binary outcomes, we implement a hierarchical generalized linear model by including a logit link for Equation (1). Note that the Level 1 error term ε_{ipsh} is also eliminated. The concatenated model for all four levels with a binary outcome then reduces to:

$$\text{logit}(Y_{ipsh}) = \beta_0 + \beta_1 \text{ARM1}_{sh} + \beta_2 \text{ARM2}_{sh} + \gamma_{1h} \text{ARM1}_{sh} + \gamma_{2h} \text{ARM2}_{sh} + \omega_1 X_{ipsh} + \omega_2 Z_{psh} + \omega_3 U_{sh} + \omega_4 W_h + \gamma_h + \eta_{sh} + \varphi_{psh} \quad (2)$$

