9.4.6 SUB-GROUP ANALYSES

We will test for heterogeneity in the treatment effect along several domains. Specifically, we will add terms interacting characteristics of the surgeon with each intervention arm and conduct an F-test of the interaction terms for each nudge.

- Specialty: We will also conduct analyses to test whether the response to each nudge varies by surgeons' specialty.
- Volume of surgeries: We will test for heterogeneity by number of surgeries performed over the 12 month study period. We will only include surgeries for which we have guidelines in this count.
- Baseline opioid prescribing: We will categorize surgeons based on the portion of their surgeries in the 12 months prior to the start of the intervention that were above guidelines. We expect that the intervention will have a larger effect for surgeon with a higher share of prescription above guidelines.

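### Section 9.3 gives no control-arm counterpart for its optional ever-nudged dataset: read literally no controls remain, and keeping all controls biases the above-guideline share against the nudges

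*Combined protocol and SAP*

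**What the plan says.** Section 9.3 makes intention to treat, with every randomized surgeon, the main analysis set. It then adds: "Sensitivity analyses may be conducted on a dataset excluding surgeons who received no nudges". Nothing more is said about that second set.

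Four other places determine what the sentence means in practice:

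- Section 6.1.1, control arm: "Surgeons randomized to the control arm will not receive any nudges and will not be informed of the study".
- Section 6.1.1, both nudge arms: "eligibility for receiving a monthly nudge is contingent upon at least two of" the surgeon's patients leaving with a prescription above guideline. Section 1.3 sets the window, with "data from the first through last day of the previous calendar month informing whether a nudge is triggered".
- Section 9.4.2, on the primary outcome: "Prescribing above guidelines is the outcome to which both nudges are linked".
- Section 9.4.2, on covariates: "Given that the covariates will not change the estimate of the treatment effect (in expectation), only reduce unexplained variance". The list that follows is open-ended and does not name the surgeon's baseline above-guideline share. Section 9.4.6 derives that quantity for a subgroup analysis, from surgeries "in the 12 months prior to the start of the intervention that were above guidelines".

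The only written comparisons based on ever having been emailed are the DSMB safety reports in section 8.2. Report 2 is set beside the ratio for all controls, and Report 3 beside all controls who were prescribed opioids.

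**The concern.** Being nudged is not a baseline characteristic. It happens only after a surgeon has produced at least two primary-outcome events in one calendar month, and only in two of the three arms. An exclusion based on it can be applied in two ways, and both fail for nudge versus control.

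1. **Applied to everyone.** No control surgeon qualifies. The coefficients β1 and β2, which are effects against control, cannot be estimated. Only the contrast between the two nudges is left.
2. **Applied to the nudge arms only.** Low prescribers and low-volume surgeons leave the nudge arms and stay in control. The remaining nudge-arm surgeons have a higher above-guideline share even if the emails do nothing. Most reference months also fall inside the outcome period, so some of the events that admit a surgeon are counted again in the outcome.

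Readers would take the result as the effect among surgeons who were actually nudged, and an effective nudge could look useless or harmful. The covariate premise in 9.4.2 rests on randomization. It does not carry over to this second set, where the answer would depend on which covariates are chosen.

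**Working it through.** **No figure in the plan to reproduce.** The check is on direction first, then on plausible size.

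**Direction, by hand.** Let a surgeon have on average m above-guideline discharges a month (volume × share), with Poisson counts. Then

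P(ever triggered in 12 months) = 1 − [e^(−m)(1 + m)]^12.

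This rises with the surgeon's share. As an illustration, assume one eligible discharge a month, half the surgeons with a share of 20% and half with 60%, and no effect of the emails:

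- 20% surgeons: m = 0.2, 1 − (0.8187 × 1.2)^12 = 0.191.
- 60% surgeons: m = 0.6, 1 − (0.5488 × 1.6)^12 = 0.790.
- Mean underlying share among triggered surgeons: (0.191 × 20% + 0.790 × 60%) / (0.191 + 0.790) = 52.2%.
- All controls: 40%. Difference with no effect: +12.2 points.

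This counts only the selection of surgeons. Re-using trigger months as outcome months adds to it.

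**Size, by simulation.** The documents give no discharge volume, no above-guideline share and no ICC for that share. The provider ICC of 0.337 in section 9.2 was estimated for medication dose, so it is used here only as one value in a range. Assumptions:

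- 250,000 surgeons per arm and scenario; surgeon ICC on the logit scale of 0.05, 0.10, 0.20 or 0.337.
- Mean eligible discharges per month of 1, 1, 2, 4, 8 (log-SD 0.8) with logit intercepts −1.5, −0.5, −0.5, −0.5, 0.5 in scenarios A to E. Control shares are then 24%, 41%, 41%, 41%, 59% at ICC 0.337 and 20%, 39%, 39%, 39%, 61% at ICC 0.10.
- Reference months September 2021 to August 2022; outcome window of 12 months from 19 October 2021; any effect starts at the surgeon's own first nudge.
- Hospital and specialty levels and patient covariates are not modelled.

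Differences are nudge minus control, in percentage points:

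| | A | B | C | D | E |
|---|---|---|---|---|---|
| **ICC 0.337**: ever nudged | 23% | 38% | 60% | 78% | 97% |
| No effect, all controls | +15.2 | +11.5 | +6.6 | +3.5 | +0.4 |
| No effect, stratified on baseline share and volume | +5.3 | +3.8 | +1.7 | +0.7 | +0.1 |
| Odds ratio 0.7, all controls | +10.6 | +6.3 | +0.8 | −2.6 | −6.0 |
| Odds ratio 0.7, intention to treat | −1.8 | −3.1 | −4.6 | −5.4 | −6.4 |
| Odds ratio 0.7, trigger in all arms | −4.6 | −5.1 | −6.0 | −6.0 | −6.5 |
| **ICC 0.10**: ever nudged | 20% | 39% | 64% | 84% | 99% |
| No effect, all controls | +7.0 | +5.0 | +2.5 | +0.7 | +0.1 |
| No effect, stratified on baseline share and volume | +4.9 | +3.7 | +1.6 | +0.4 | 0.0 |
| Odds ratio 0.7, all controls | +3.3 | −0.6 | −3.9 | −6.0 | −7.9 |
| Odds ratio 0.7, intention to treat | −1.4 | −3.6 | −5.3 | −6.5 | −7.9 |
| Odds ratio 0.7, trigger in all arms | −3.7 | −5.6 | −6.3 | −6.9 | −7.9 |

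At ICC 0.05 the no-effect bias with all controls was still +5.2, +3.8, +1.6, +0.6, 0.0. With the trigger applied in all arms, the no-effect difference was within 0.2 points of zero in all 20 scenario-by-ICC combinations.

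**On the scale of a logistic model.** A surgeon random-intercept logistic model, simpler than Equation (2), with no effect and all controls kept gave odds ratios of 3.28, 2.26, 1.78, 1.35, 1.02 at ICC 0.337. Adding baseline share and volume as covariates lowered them to 1.59, 1.36, 1.15, 1.05, 1.00. At ICC 0.10 they were 1.68, 1.35, 1.17, 1.08, 1.02, lowered to 1.51, 1.26, 1.09, 1.03, 1.01. The matched-trigger odds ratios were 0.97 to 1.03.

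**A different model.** A beta-binomial simulation (shares 20/40/60%, 1/3/8 discharges a month, ICC 0.15 and 0.337) gave a no-effect excess of +0.1 to +26.6 points over 18 scenarios. With a true 20% relative reduction the sign was wrong in 9 of 18 with all controls and right in all 18 with matched controls. The bias stayed positive when volume and share were made negatively correlated (+1.1 to +37.3 points, 27 scenarios).

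The unadjusted table figures were reproduced by separate simulation to within about 0.3 points. The stratified and random-intercept figures come from one run.

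**The case against.** The best defence is that nothing planned has been shown to be wrong. The analysis is optional, and no hypothesis, power statement or decision depends on it. Sections 9.4.1 and 9.4.2 define effects relative to control, so an ordinary reader would not delete the control arm, and the authors may intend a matched control set. The covariate list is open and could take in baseline share. The safety reports are descriptive and do not show how an efficacy set would be built. The size of the bias rests on assumed inputs. Section 4.3 says that the number of surgeons who would be nudged was simulated from the system's own data, so the sponsor can judge the size better than this review can.

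Most of this stands and sets the severity. If nearly all surgeons are nudged, the bias is trivial, as scenario E shows. It does not remove the point. A matched set is possible but is not written. Choosing the control set after results are seen is a risk in itself. Covariate adjustment on baseline share and volume reduces the bias but leaves +5.3 points (ICC 0.337) or +4.9 points (ICC 0.10) in scenario A.

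**Conclusion.** The concern holds, at low severity. As written, the 9.3 dataset gives either no nudge-versus-control estimate or, with all controls kept, one biased against the nudges on the above-guideline share. The direction follows from the trigger and was never negative in any scenario. The size depends on assumed volume, share and ICC: from about zero when almost every surgeon is nudged to +15.2 points (main model) when 23% are. A true odds ratio of 0.7 changes sign in three of five scenarios at ICC 0.337 and one of five at 0.10. In the random-intercept model it shows an odds ratio above 1 in four of five and two of five (two and one with baseline covariates).

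Not affected: the intention-to-treat analysis and, largely, nudge versus nudge, because both nudge arms share one trigger. The direction for emergency visits, hospitalizations and other outcomes is not established.

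**What to change.** In section 9.3, define the set by meeting the trigger rather than by receiving an email, and apply it identically in all three arms: surgeons with at least two above-guideline discharges in at least one reference month from September 2021 to August 2022. For controls, compute from the EHR whether they would have been nudged. A surgeon's first trigger comes before that surgeon's first nudge, so the status is comparable across arms unless nudged colleagues influence it.

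If such spillover is a worry, define the set from the 12 whole months October 2020 to September 2021, which lie inside the baseline period of section 9.4.4. The price is that it only approximates who was nudged: across scenarios A to E it captures 64%, 71%, 83%, 91%, 98% of nudged surgeons at ICC 0.337 and 54%, 68%, 82%, 92%, 99% at ICC 0.10. The choice should be stated before outcome data are seen.

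Use the same control flag to add a like-for-like control row to safety Reports 2 and 3.

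Cost: one sentence in 9.3, a short edit to 8.2 for the added rows, and running the recipient-list code, already independently programmed twice (section 6.2.4), on control surgeons, with the flag refreshed for the monthly reports. No new data are needed.
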